#### PFIZER CONFIDENTIAL

Page 100

**Prohibited Medications Dependent on CYP450 3A4 for Clearance or with other Notable Interactions**a These medications are prohibited *from the first dose* of PF-0321332/placebo and ritonavir/placebo, through 4 days after the last dose of PF-07321332/placebo and ritonavir/placebo. If a participant cannot temporarily interrupt the prohibited medication during this period, they should be considered ineligible.

Drug Class	Specific Medication	Clinical Comments
Alpha 1-Adrenoreceptor	Tamsulosin, silodosin, doxazosin	Risk of hypotension, syncope
Antagonist	(>2 mg daily), terazosin (>5 mg	
-	daily),	
Analgesics	Methadone	Moderate to weak decreases in methadone concentrations have been observed
	Fentanyl, oxycodone	Analgesic concentrations may increase
	Buprenorphine Lofexidine	
Opioid Dependence Treatment	Lotexidine	Co-administration may increase concentrations of buprenorphine and lofexidine
Anesthetic	Pethidine (Meperidine)	
		Co-administration with ritonavir may result in increase in concentration of the metabolite normeperidine
Antiarrhythmics	Amiodarone, Bepridil, Flecainide, Propafenone, Quinidine, Encainide, Disopyramide, dofetilide, lidocaine, mexiletine	Risk of cardiac arrhythmias
Anticoagulants/ antiplatelet	Rivaroxaban, Vorapaxar, apixaban, betrixaban, dabigatran, edoxaban ticagrelor	Possible increased risk of bleeding
	Warfarin	
		Possible decreased warfarin effects
Anticonvulsants	Ethosuximide Eslicarbazepine Oxcarbazepine Phenobarbital	Co-administration may increase these anticonvulsant concentrations or decrease PF-07321332 and ritonavir concentrations
	Lamotrigine Divalproex Valproate	Co-administration may decrease concentration of lamotrigine, divalproex, and valproate

**Prohibited Medications Dependent on CYP450 3A4 for Clearance or with other Notable Interactions**a These medications are prohibited *from the first dose* of PF-0321332/placebo and ritonavir/placebo, through 4 days after the last dose of PF-07321332/placebo and ritonavir/placebo. If a participant cannot temporarily interrupt the prohibited medication during this period, they should be considered ineligible.

Drug Class	Specific Medication	Clinical Comments
Antidepressant	Desipramine, Fluoxetine, Paroxetine nefazodone, Amoxapine, Clomipramine, Doxepin, Imipramine, Maprotiline Amitryptiline, nortryptiline, protryptiline, Trimipramine, aripiprazole	May increase antidepressant concentration
Anti-infective (antibacterials)	Erythromycin	Co-administration may increase erythromycin concentrations.
	Clarithromycin	Co-administration may increase clarithromycin concentrations.
(antimycobacterials)	Bedaquiline	Co-administration may increase bedaquiline concentrations
	Rifabutin	Co-administration may increase rifabutin concentrations
(antifungals)	Isavuconazole Itraconazole Posaconazole Ketoconazole Voriconazole	Possible increased concentrations of antifungal, of PF-07321332, or both.
		Co-administration of ritonavir with voriconazole may result in reduction in voriconazole levels
Antihistamines	Astemizole, Terfenadine	Risk of cardiac arrhythmias
Antipsychotics	Quetiapine Risperidone, Perphenazine,	Co-administration may increase quetiapine and increase risk of quetiapinerelated toxicity. Potential for increased levels of antipsychotics.
	aripiprazole, brexpiprazole, cariprazine, Iloperidone, perphenazine, risperidone, thioridazine, ziprasidone	
Cardiac Medications (beta blockers)	Carvedilol, metoprolol, timolol	Co-administration may increase concentration of carvedilol, metoprolol, timolol

#### **Prohibited Medications Dependent on CYP450 3A4 for Clearance or with other Notable Interactions**a These medications are prohibited *from the first dose* of PF-0321332/placebo and ritonavir/placebo, through

4 days after the last dose of PF-07321332/placebo and ritonavir/placebo. If a participant cannot temporarily interrupt the prohibited medication during this period, they should be considered ineligible.

Drug Class	Specific Medication	Clinical Comments
(calcium channel blockers)	Diltiazem, Verapamil, Nifedipine, amlodipine (> 5 mg daily)	Co-administration may increase concentrations of calcium channel blockers. The impact on the PR interval of co- administration of ritonavir with other drugs that prolong the PR interval (including calcium channel blockers) has not been evaluated.
(cardiac glycosides)	Digoxin	Co-administration increases digoxin concentrations.
	Eplerenone	Co-administration increases eplerenone concentrations
	Ranolazine	Co-administration increases ranolazine concentrations
	Ivabradine	Co-administration increases ivabradine concentrations
Corticosteroids (inhaled or intranasal)	Budesonide, ciclesonide, mometasone	Co-administration can increase concentration of budesonide, ciclesonide, and mometasone and can result in adrenal insufficiency and Cushing's syndrome.
(systemic)	Betamethasone Budesonide	Co-administration can increase concentration of betamethasone, and budesonide and can result in adrenal insufficiency and Cushing's syndrome.
(Local injections, including intra- articular, epidural, or intra-orbital)	Betamethasone, methylprednisolone, triamcinolone	Co-administration can increase betamethasone, methylprednisolone, and triamcinolone concentrations and can result in adrenal insufficiency and Cushing's syndrome
Endothelin receptor antagonists	Bosentan	Bosentan should be discontinued at least 36 hours prior to the initiation of ritonavir

**Prohibited Medications Dependent on CYP450 3A4 for Clearance or with other Notable Interactions**a These medications are prohibited *from the first dose* of PF-0321332/placebo and ritonavir/placebo, through 4 days after the last dose of PF-07321332/placebo and ritonavir/placebo. If a participant cannot temporarily interrupt the prohibited medication during this period, they should be considered ineligible.

Drug Class	Specific Medication	Clinical Comments
Ergot Derivatives	Ergonovine	Risk of acute ergot toxicity (peripheral vasospasm and ischemia of the extremities)
Hepatitis C direct acting antivirals (DAAs)	Boceprevir, Glecaprevir/Pibrentasvir Simeprevir, Sofosbuvir/Velpatasvir/Voxilaprevir, Ombitasvir/Paritaprevir/ritonavir/ Dasabuvir, Grazoprevir/elbasvir	Co-administration can increase plasma concentrations of select DAAs
HIV Antiretrovirals Protease Inhibitors	Lopinavir, Amprenavir, Indinavir, Nelfinavir, Atazanavir, Darunavir, fosamprenavir, saquinavir, tipranavir.	Co-administration may increase HIV protease inhibitor concentrations.
	Ritonavir or cobicistat containing combination products	Risk of increased rate of adverse reactions. Appropriate doses of additional ritonavir in combination with ritonavir-containing combination products with respect to safety and efficacy have not been established.
Integrase Inhibitors	Elvitegravir	Co-administration will increase elvitegravir concentrations
Lipid lowering drugs (HMG-CoA Reductase Inhibitors)	Atorvastatin (>20 mg daily), Rosuvastatin (>10 mg daily)	Risk of rhabdomyolysis
	Lomitapide	Co-administration may increase concentration of lomitapide
Hypoglycemics	Glipizide, Tolbutamide	Potentially decrease glipizide and tolbutamide concentrations
	Repaglinide	Potentially increase repaglinide concentrations
	Saxagliptin (>2.5 mg daily)	Co-administration may increase saxagliptin concentration
Immunosuppressants	Cyclosporine, Tacrolimus, Sirolimus, everolimus	Co-administration may increase immunosuppressant concentrations

Prohibited Medications Dependent on CYP450 3A4 for Clearance or with other Notable Interactions a		
These medications are prohibited from the first dose of PF-0321332/placebo and ritonavir/placebo, through		
4 days after the last dose of PF-07321332/placebo and ritonavir/placebo. If a participant cannot temporarily		
interrupt the prohibited medication during this period, they should be considered ineligible.		
Drug Class Specific Medication Clinical Comments		

Drug Class	Specific Medication	Clinical Comments
Long-Acting Beta- Adrenoceptor Agonist	Salmeterol	The combination may result in increased concentrations of salmeterol and increased risk of cardiovascular adverse events, including QT prolongation, palpitations and sinus tachycardia
Neuroleptic	Pimozide	Risk of cardiac arrhythmias
Sedatives/ Hypnotics	Midazolam (parenteral), alprazolam, bromazepam, brotizolam, clonazepam, cloniprazepam, delorazepam, diazepam, etizolam, eszopiclone, halazepam, lormetazepam, nitrazepam, nordiazpam, quazepam, suvorexant, temazepam, zaleplon, zolpidem	Risk of prolonged sedation, respiratory depression, or hypnotic concentrations
	Clorazepate, estazolam, flurazepam,	
	Zolpidem (> 5mg daily)	Co-administration with ritonavir may increase dose of clorazepate, estazolam, and flurazepam. Co-administration may increase
		zolpidem concentration
Miscellaneous Drugs	Cisapride	Co-administration may result in increased cisapride concentration and possible cardiac arrhythmias
	Dronabinol	Co-administration may increase dronabinol concentration
	Eluxadoline (>75 mg twice daily)	Co-administration may increase eluxadoline concentration
	Flibanserin	Co-administration may increase flibanserin concentration.

a. Note: If a drug is not listed, it should not automatically be assumed it is safe to co-administer.

Hormonal Contraceptives: Estradiol-containing hormonal contraceptive medications can be continued while receiving investigational product, but their effectiveness may be impacted. Therefore, barrier methods of contraception must be used for at least one full menstrual cycle following completion of investigational product dosing.

Medications may be used with caution and require oversight by the investigator when co-administered with PF-07321332/ritonavir a		
Drug Class	Specific Medication	Clinical Comments
Antidepressant	Citalopram, escitalopram	No data available
	Sertraline, Bupropion	Co-administration may decrease sertraline and bupropion concentrations
	Trazodone	Co-administration with ritonavir increases the level/effect of trazodone by affecting hepatic/intestinal enzyme CYP3A4 metabolism. Further, trazodone may decrease the level/effect of ritonavir by P- glycoprotein (MDR1) efflux transporter. To be used with caution.
Anticancer Agents:	Dasatinib, imatinib, nilotinib, venetoclax, Vincristine, Vinblastine	Co-administration of ritonavir may increase the concentration of dasatinib and nilotinib. Coadministration of ritonavir with venetoclax may increase concentration of venetoclax and increase the risk of tumor lysis syndrome.
		Con-administration with ritonavir may increase the concentrations of vincristine and vinblastine and develop significant hematologic or gastrointestinal side effects.
Antihypertensive Angiotensin receptor blockers:	Losartan, valsartan	Co-administration with ritonavir increases the level/effect of losartan by affecting hepatic/intestinal enzyme CYP3A4 metabolism. Ritonavir increases the level/effect of valsartan by decreasing hepatic clearance. To be used with caution.
Antiparasitic:	Atovaquone	Co-administration with ritonavir may decrease the concentration of atovaquone
	Quinine	Co-administration with ritonavir may decrease concentration of quinine

Drug Class	Specific Medication	Clinical Comments
Antipsychotic:	Haloperidol	Co-administration with ritonavir increases the level/effect of haloperidol by affecting hepatic/intestinal CYP3A4 metabolism. Haloperidol and ritonavir both increase QTc interval. To be used with caution.
Bronchodilator:	Theophylline	Co-administration with ritonavir may decrease theophylline concentration.
Corticosteroids	Fluticasone	RTV twice daily increases fluticasone AUC 350-fold
HIV Antivirals	Delavirdine	Co-administration may increase ritonavir concentration
Non-nucleoside reverse transcriptase inhibitors	Maraviroc	Co-administration may increase maraviroc concentration
CCR5-antagonist	Raltegravir	Raltegravir concentrations may be decreased
Integrase inhibitors		
Hypoglycemics	Canagliflozin	Co-administration may decrease canagliflozin concentration
Narcotic and Treatment for Opioid Dependence	Tramadol	Co-administration may increase concentration of tramadol
PDE-5 Inhibitors for treatment of erectile dysfunction	Sildenafil – ED (max dose 25 mg every 48 hours) Avanafil Tadalafil (max dose 10 mg every 72 hours) Vardenafil (max dose 2.5 mg every 72 hours)	Risk of visual disturbances, hypotension, prolonged erection, and syncope
Steroids (systemic)	Dexamethasone Prednisone	Co-administration with ritonavir may increase dose of dexamethasone and prednisone and may increase the risk for development of systemic corticosteroid effects including Cushing's syndrome and adrenal suppression

Medications may be used with caution and require oversight by the investigator when co-administered

Medications may be used with caution and require oversight by the investigator when co-administered with PF-07321332/ritonavir a		
Drug Class	Specific Medication	Clinical Comments
Stimulant	Methamphetamine	Co-administration with ritonavir may increase concentration of methamphetamine

a Note: If a drug is not listed, it should not automatically be assumed it is safe to co-administer

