# 10.8. Appendix 8: Prohibited Concomitant Medications That May Result in DDI

PF-07321332 and ritonavir are both primarily metabolized by CYP3A4. Therefore, concomitant use of any medications or substances that are strong inducers of CYP3A4 are prohibited within 28 days prior to dosing of study intervention and during study treatment.

Additionally, ritonavir and PF-07321332 are inhibitors of CYP3A4. Therefore, medications highly dependent on CYP3A4 for clearance and for which elevated plasma concentrations may be associated with serious and/or life-threatening events are not permitted during dosing of PF-07321332/ritonavir (at least 24 hours prior to the first dose of study intervention or as late as Day 1, prior to the first dose of study intervention – see below) and for 4 days after the last dose of PF-07321332/ritonavir. Ritonavir also appears to induce CYP3A, CYP1A2, CYP2C9, CYP2C19, and CYP2B6 as well as other enzymes, including glucuronosyl transferase. Since ritonavir 100 mg q12h is being used to boost the exposure of PF-07321332, no additional DDI is expected other than those associated with ritonavir 100 mg q12h based on in vitro assessments.

A nonexhaustive list of prohibited and precautionary medications is provided below. If a medication is not listed, it should not automatically be assumed it is safe to co-administer. Appropriately qualified site staff will review all concomitant medications to determine if they are prohibited.

The Pfizer study team is to be notified of any prohibited medications taken during the study. After consulting with the sponsor, the investigator will make a judgement on the ongoing participation of any participant with prohibited medication use during the study.

This list of drugs prohibited for potential DDI concerns with the IMP may be revised during the course of the study with written notification from sponsor, to include or exclude specific drugs or drug categories for various reasons (eg, emerging DDI results for the IMP, availability of new information in literature on the DDI potential of other drugs).

This is not an all-inclusive list. Site staff should consult with the sponsor or designee with any questions regarding potential DDI.

r	during dosing of PF-07321332/placebo	and monavii/placebo.
Drug Class	Specific Medication	Clinical Comments
Anti-infectives	Rifampin	Reduced concentrations of PF-
Anticonvulsants	Phenytoin, Carbamazepine	07321332/ritonavir; may result in

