Herbal Products	St. John's Wort	suboptimal concentrations
Prohibited Medications D	ependent on CYP450 3A4 for Cleara	nce or with other Notable
Interactions a		
These medications are proh	nibited for at least 24 hours prior to the	first dose of PF-0321332/placebo
and ritonavir/placebo, throu	igh 4 days after the last dose of PF-073	21332/placebo and ritonavir/placebo.
If a participant cannot temp considered ineligible.	porarily interrupt the prohibited medicat	ion during this period, they should be
Drug Class	Specific Medication	Clinical Comments
Alpha 1-Adrenoreceptor	Alfuzosin	Risk of hypotension, syncope
Antagonist		
Analgesics	Piroxicam, propoxyphene	Analgesic concentrations may
		increase
Antianginal	Ranolazine	Risk of cardiac arrhythmias
Antiarrhythmics	Dronedarone	Risk of cardiac arrhythmias
Antipsychotics	clozapine, lurasidone, pimozide	Potential for increased levels of
		antipsychotics.
Ergot Derivatives	Dihydroergotamine, ergotamine,	Risk of acute ergot toxicity
	methylergonovine	(peripheral vasospasm and
<del>.</del>		ischemia of the extremities)
Lipid lowering drugs (HMG-CoA Reductase Inhibitors)	Lovastatin, simvastatin	Risk of rhabdomyolysis
PDE-5 Inhibitors for pulmonary arterial	Sildenafil (Revatio) when used for pulmonary arterial hypertension	Risk of visual disturbances,
hypertension treatment		Co-administration may result in
		visual abnormalities,
		hypotension, prolonged erection,
		and syncope
Sedatives/	Triazolam, oral midazolam	Risk of prolonged sedation,
Hypnotics		respiratory depression, or
		hypnotic concentrations
Miscellaneous Drugs	Colchicine	Ritonavir 100 mg twice daily
		increased colchicine AUC 296%
		and C max 184%. Potential for
		serious and/or life-threatening
		reactions in patients with renal
		and/or hepatic impairment.

a. Note: If a drug is not listed, it should not automatically be assumed it is safe to co-administer.

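### Protocol Appendix 8 gives conflicting prohibition rules for four drugs: on the pre-dose interval for ranolazine, pimozide and bosentan, and on the dose limit for zolpidem

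*Protocol*

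**What the plan says.** The introductory text of Protocol Section 10.8 (Appendix 8) sets two start times for drugs that depend on CYP3A4 for clearance: "at least 24 hours prior to the first dose of study intervention or as late as Day 1", before the first dose, depending on the table that follows.

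- **The 24-hour table.** Its drugs are prohibited "for at least 24 hours prior to the" first dose and through 4 days after the last dose. It lists ranolazine as an antianginal and pimozide in the antipsychotic row ("clozapine, lurasidone, pimozide").
- **The from-first-dose table.** Its heading reads "These medications are prohibited *from the first dose* of PF-0321332/placebo and ritonavir/placebo, through" 4 days after the last dose. It lists ranolazine again among the cardiac medications ("Co-administration increases ranolazine concentrations") and pimozide again as a neuroleptic.
- **Bosentan** is listed once, in the from-first-dose table, with the comment "Bosentan should be discontinued at least 36 hours prior to the initiation of ritonavir".
- **Zolpidem** is listed twice in the from-first-dose table. It closes the general sedative list with no dose condition ("suvorexant, temazepam, zaleplon, zolpidem") and then appears as a separate item with one ("Zolpidem (> 5mg daily").

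Both table headings add that a participant who cannot temporarily interrupt the drug over the stated period is ineligible. Exclusion criterion 11 in Section 5.2 refers to this appendix.

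**The concern.** These entries are operative rules. Site staff use them to decide whether a participant may be randomized and when the first dose may be taken. Section 5 permits no eligibility waivers, Section 7.1 makes the need for a prohibited drug a reason to stop study intervention, and Appendix 8 requires prohibited use to be notified to the sponsor.

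If one drug carries two rules, two sites can treat the same medication history differently and both be following the protocol. They can also differ on whether they report a deviation. The duplicates sit under different drug-class labels (antianginal and cardiac medication, antipsychotic and neuroleptic), so staff who search by class can find one entry and miss the other.

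There is a safety side. The appendix gives cardiac arrhythmia as the risk in the ranolazine row of the 24-hour table and in the pimozide row of the from-first-dose table. The other row for each drug mentions only raised concentrations or levels.

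**Working it through.** The plan states no figure to reproduce here. The check is to look up each drug in every Appendix 8 table, set its entries side by side, and find where they give different answers.

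Let *t* be the hours between the last intake of the drug and the first dose of study intervention, for a participant who then stops it. Let *d* be the daily zolpidem dose in mg.

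| Drug | Entry 1 | Entry 2 | Entries disagree when |
|---|---|---|---|
| Ranolazine | 24-hour table: needs *t* ≥ 24 | From-first-dose table: needs *t* > 0 | 0 < *t* < 24 |
| Pimozide | 24-hour table: needs *t* ≥ 24 | From-first-dose table: needs *t* > 0 | 0 < *t* < 24 |
| Bosentan | Row comment: needs *t* ≥ 36 | Heading of the same table: needs *t* > 0 | 0 < *t* < 36 |
| Zolpidem | General sedative row: prohibited for any *d* > 0 | Separate item: prohibited for *d* > 5 | 0 < *d* ≤ 5 |

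1. **Count.** Three drugs conflict on timing and one on dose: 3 + 1 = 4.
2. **Size of the timing gaps.** 24 − 0 = 24 hours for ranolazine and for pimozide, and 36 − 0 = 36 hours for bosentan. The bosentan interval matches neither start time in the introductory text; it is 36 − 24 = 12 hours longer than the longer of the two.
3. **End of the prohibition.** Both tables run through 4 days after the last dose. For ranolazine, pimozide and bosentan, use during dosing and for those 4 days is therefore prohibited whichever entry is followed.
4. **Zolpidem timing.** Both entries are in one table, with the same start and the same end, so there is no difference in washout. Dose limits carry meaning in this table: amlodipine, atorvastatin, rosuvastatin and saxagliptin are prohibited only above stated doses. The two zolpidem rows therefore give opposite answers at 5 mg daily or less and the same answer above it.
5. **Can the timing gap be reached in practice?** Yes. The Schedule of Activities allows screening, randomization and the first dose on one calendar day. A participant who took ranolazine or pimozide that morning fails the 24-hour table but can satisfy the from-first-dose table by stopping before dosing. A participant who took bosentan that morning fails the row comment but can satisfy the heading.
6. **Does other text settle it?** No. Exclusion criterion 11 and Section 6.8 cover use during treatment and for 4 days after, and give no pre-dose interval for these drugs. Neither mentions zolpidem or a dose limit for it. No sentence says that one table, or a row comment, takes precedence.

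**The case against.** The strongest reply is that the conflict is narrow and the protocol has safeguards.

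- **The start rules are nested.** Stopping 24 hours ahead also satisfies the from-first-dose rule, so a site that meets the longer interval meets both. This is correct and it limits the point to the windows in the table above. It does not remove the point, because the protocol does not say that the longer interval governs.
- **Screening may take up to 48 hours** (Section 4.1), so the practical effect may be only a later first dose. That may often be so, but same-day dosing is expressly allowed, and the decision then turns on which row was read.
- **Bosentan is a different kind of problem.** It has one row with an explicit instruction, and a drug-specific comment can be read as adding to a general heading. That is a reasonable reading. The heading still states another start time, and the introductory text provides for no 36-hour tier.
- **Staff review and sponsor advice.** Qualified staff review concomitant medication before the first dose (Section 6.8), and Appendix 8 tells sites to consult the sponsor with questions. This helps only when staff notice both entries.

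A reader might infer that all four drugs have conflicting washouts. The documents do not support that for zolpidem, whose two rows share one window. A reader might also infer from the arrhythmia comments that use of ranolazine or pimozide alongside study treatment is left open. It is not: every entry prohibits it.

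**Conclusion.** The point holds as an internal inconsistency in the eligibility and concomitant-medication rules. Four drugs are affected. For ranolazine and pimozide the entries differ for intake within 24 hours before the first dose. For bosentan the row comment and the table heading differ for intake within 36 hours before. For zolpidem the rows differ on whether 5 mg daily or less is prohibited.

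It should not be read as saying that a participant on any of these drugs is in general eligible under one row and ineligible under another. For the first three drugs that can arise only inside the windows above, because both headings exclude anyone who cannot interrupt the drug.

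The documents do not give the number of participants on these drugs, so the practical frequency is unknown and may be small. The endpoint, estimand, sample size, power and type I error are not touched. The conclusion assumes that dose limits in the table are meant literally and that no document outside the protocol and SAP sets an order of precedence. Amendment 3 records corrections to this appendix, but the conflicts remain in the current text. The inconsistency should be corrected because the rules bear on safety and the correction is cheap.

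**What to change.** Reconcile Appendix 8 so that each of the four drugs has one entry, one start time and one dose condition, and so that each row comment agrees with the heading of its table. If a drug needs an interval that neither table provides, the heading or the introductory text should say so. A search of the whole appendix for other drugs listed more than once would be sensible at the same time.

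The sponsor's clinical pharmacology group must decide which entry stands; nothing here favors one over another.

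The cost is small: a wording change in an amendment, or the written notification to sites by which Appendix 8 already allows the list to be revised. No analysis, sample size or SAP text has to change.
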